## 2.1.2. Escitalopram

Escitalopram is a highly selective serotonin reuptake inhibitor (SSRI) that was licensed in the US in 2002 as an approved treatment for major depressive disorder. It has since been prescribed to millions of people worldwide, becoming a gold-standard medication for depression. Meta-analyses have indicated that escitalopram is one of the best performing SSRIs in terms of tolerability and efficacy [77] and it is one of the most selective SSRIs [78].

Patients in condition 2 who receive an inactive dose of psilocybin (1mg) during the first dosing day, will subsequently receive 6 weeks of daily escitalopram. For the first 3 weeks they will receive 10mg-daily (1 capsule per day). After 3 weeks they will have a second 1mg psilocybin dosing day (without interrupting the daily escitalopram dosing schedule). After this, they will subsequently take 20mg of escitalopram daily (2 capsules per day) for three further weeks. The dose of 20mg is the recommended maximum dose for this commonly prescribed primary treatment for depression, and thus we would expect the patient's symptoms of depression to decrease. It would be expected that patients starting a course of SSRIs would report some improvements in depressive symptoms after even this relatively brief treatment period of 6 weeks [80, 81].

The dose of escitalopram can be lowered to 10mg from 20mg if patients appear not to be tolerating 20mg and ask to lower the dose or withdraw from the trial. This would be simple to implement as we would just instruct patients to take 1 capsule daily instead of 2. If, when the blind is broken at the 6 week endpoint, it transpires that the patient was actually in condition 1 and not in fact in the escitalopram condition, this would be logged.

We will be monitoring patients' response to escitalopram via weekly self-report measures, and measures of side effects. FDA guidelines report the following possible side-effects with escitalopram: headaches, dizziness, nausea, insomnia, dry mouth, impotence, decreased appetite, weight gain, vomiting, vivid dreams and a tingling sensation in arms, hands, feet and legs [79]. Insomnia and diarrhea are the most common side-effects, affecting 15% of individuals at 20mg [79].

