## Contraindicated medications for escitalopram include [86, 87]:

- MAOIs
- Procarbazine

- NSAIDs (including) Aspirin should be avoided during the course of the trial, as they may cause GI bleeding [86].

- Medicines that prolong QT interval, including [99]:

- Cardiac medications: Class 1a (Quinidine, Procainamide, Disopromide) and Class III (Dofetilide, Ibutilide, Sotalol) Antiarrythmic drugs
- Antihistamines (Terfenadine, Astemizole)
- Antipsychotics: Haloperidol, Droperidol, Thioridazine, Sertindole\*, Ziprasidone, Risperidone, Zimeldine, Chlorpromazine
- Antidepressants: Citalopram, Amitriptyline, Desipramine, Imipramine, Maprotiline, Doxepin, Fluoxetin
- Antibiotics: Quinolone (Sparfloxacin, Levofloxacin, moxifloxacin, grepafloxacin) and Macrolide (Erythromycin, Clarithromycin)
- Antimalarials (Quinine, halofantrine)
- Antiprotozoal (Pentamidine)
- Antifungal (Azole group)
- Antimotility agents (Cisapride)
- Methadone

Antipsychotic medications and mood stabilisers may attenuate the effects of psilocybin and so are also contraindicated for this reason. However, such medications are usually only prescribed for manic and/or psychotic illness, and patients presenting with such histories would be excluded from the study. Details regarding discontinuation of antidepressant medications can be found below (2.4.1).

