#### Visit 2: Scan 1/Prep

The scanning procedure takes approximately 2.5 hours, with the scan itself lasting for no longer than 90 minutes. The scan session will be followed by psychological preparation with the therapy team (two individuals) who will sit with the patient during their dosing session. Psychological preparation will take approximately 3 hours, with two breaks. This visit will take approximately **5.5 hours** in total.

#### Visit 3: Dosing session 1

The dosing session will take place the day after scan 1. Depending on the results of randomisation, the patient will receive either 25mg (conditions 1) or 1mg psilocybin (condition 2) in the morning. After their dosing session is over, they will be given either placebo capsules (condition 1) or 10mg escitalopram capsules (condition 2) to take home with them. The dosing day will typically run for ~8 hours and involve: arrival at 9am, initial preparation, including relaxation techniques. Dosing at 10:30am. Drug effects (25mg only) are typically experienced for 5-6 hours (i.e. subsiding to a low-negligible level at 3:30-4:30pm). Depending on the magnitude of residual drug effects, patients will be asked to complete questionnaires from 3:30pm onwards and take part in a filmed and audio recorded structured interview at ~4:30/5pm (consent for this is included in the consent sheet – and with consent, all visits will be filmed as default). A study psychiatrist will assess the patient for potential discharge. If the patient is to travel home, a taxi will be ordered. Patients will typically leave the study centre around 5:30/6:00pm.

[figure not shown]

Fig 2. Dosing day timeline

At the end of the first dosing session, patients will be given a course of capsules to be taken daily (upon waking) for the following 6 weeks. Randomisation will determine whether these capsules are to be escitalopram or placebo. Patients will be asked to take their first capsule as close to **8:00am** as possible the morning after the first dosing session and document exactly when it was taken, to ensure standardisation of peak plasma concentration where relevant (i.e. escitalopram condition). N.B. peak plasma concentrations of escitalopram are reached 3-4 hours post-ingestion [10]. Each patient will take one capsule each day for the first 3 weeks and two for the remaining 3 weeks, regardless of whether they are in condition 1 or 2.

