## Rare (prevalence unknown but likely < 2%):

- 1) HPPD/flashbacks
- 2) Worsening of mental state after the drug experience

It is not uncommon for people to experience some negative psychological content during a psilocybin 'trip', particularly if they suffer from ongoing psychological distress, as is characteristic of depression. Typically, this is best deal with by good preparation and support during the experience and integration afterwards. In our sample of 20, while challenging episodes were relatively common within the patients' trips, none were entirely characterized by dysphoric or distressing content, and when challenging content did arise, it was often worked through and contributed to a psychological 'breakthrough' on the part of the patient. Recent evidence indicates that challenging psychological experiences can produce therapeutic benefits, improving psychological well-being in the long-term [69].

Negative aftereffects of challenging psychological experiences under psychedelics are thought to be a consequence of inadequate 'set and setting' and post-session integration work – and they may also relate to the duration of the challenging period [69]. We shall reduce these risk through good psychological preparation and integration work, good patient-staff rapport and a positive environment. Research and medical staff will plan carefully for such eventualities however. Challenging experiences/periods are best managed psychologically. Injectable lorazepam, as a 'rescue medication', will be available but would only be used in cases of severe panic that were unresponsive to psychological intervention, and where the patient's behavior was putting themselves and/or staff in danger. Consent for such medication will be sought from the patient ahead of study participation. Detailed protocols are available on the safe management of clinical research with psychedelics [70].

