## Less common (< 10%)

- 1) Frequent urination
- 2) Indigestion
- 3) Increased or decreased appetite
- 4) Taste alterations
- 5) Tremor (shaking)
- 6) Tingling in arms or legs
- 7) Weight changes
- 8) Influenza-like symptoms and pain in neck or shoulders
- 9) Serotonin syndrome
- 10) Suicidal thinking and behavior
- 11) Abnormal bleeding
- 12) Seizures
- 13) Manic episodes
- 14) Low sodium
- 15) Angle closure glaucoma

The MHRA recommends that escitalopram should not be used in patients with known QT interval prolongation (above 440ms in men and above 470ms in women) or in combination with other medicines known to prolong the QT interval. An ECG during the screening visit will ensure that such individuals will be excluded from the study. To prevent antidepressant discontinuation syndrome, gradual withdrawal from escitalopram will be managed by the study psychiatrist in consultation with the patient's GP/psychiatrist.

In the event of signs of cardiac arrhythmia (fluttering in chest, tachycardia, bradycardia, chest pain, shortness of breath, lightheadedness, etc), patients will be advised to contact us and their GP immediately and stop escitalopram dosing. In this case, we would schedule an extra visit and perform an extra ECG.

Additionally, the Summary of Product Characteristics (SmPC) for escitalopram [100] advises caution in patients with severely reduced renal function (CLCR less than 30 ml/min). We are aiming to recruit depressed patients who are otherwise physically healthy and will be excluding patients with severely reduced renal function as per exclusion criteria.

The SmPC for escitalopram [100] also raises cautions about its use in patients with hepatic impairment. In the case of mild or moderate hepatic impairment, dose reduction is necessary. For consistency, patients with any form of hepatic impairment will be excluded (see section 4.2.4). Liver Function Tests (LFTs) conducted in screening will provide the study medical doctor with the necessary information to make this assessment.

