- Typical doses administered would be PO 1-2mg Lorazepam initially then titrated to effect, but any benzodiazepine or tranquilising medication may be administered. This medical decision lies with the full-time trial clinicians present at the time, all ILS trained.
- If such an adverse event was to occur, a member of staff will accompany the patient at all times and in no circumstances will they be permitted to leave the unit until the psychiatrist is satisfied that they are in a fit state to do so.
- We foresee the majority of patients being able to return home approximately 6 hours after receiving the drug; however, there may be patients who we feel are not in the appropriate frame of mind to be discharged from the clinical research facility at that time. If this was to occur, a psychiatrist would remain in the department for as long as is necessary to ensure the patient's recovery back to their previous level of functioning.
- Prior to a patient's discharge from the unit, an assessment of their current level of risk will be conducted to determine whether it is safe for them to leave.
- Should we have any reservations about discharging a patient, they will be offered the option of an overnight stay at a nearby facility until the following day. They will be supported overnight by the psychiatrist and research nursing staff.
- Patients will be reviewed the next morning to establish whether they have returned to their normal level of functioning and we will decide whether they can return home.
- Phone numbers for each member of the research team will be provided to the patient and this responsible other to ensure immediate contact if required. We will also have contact details for the patient and their responsible other, if we need to be in contact.
- Appropriate follow-ups are in place for monitoring the patient's status throughout the study and afterwards. We will therefore be able to detect any prolonged or delayed adverse events.

 Patients and their relatives will be encouraged to contact us should their mental or physical health deteriorate. Although our options of managing their current difficulties will be limited after the trial is complete, we will be able to offer referral to the relevant services. If indicated, we will offer a further follow-up at the clinical research facility so that we can review the patient in person.

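### Section 8 allows any tranquillising drug as rescue, without excluding the QT-prolonging antipsychotics that section 2.3.2 contraindicates with escitalopram; the overlap arises mainly at dosing session 2

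*Protocol*

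**What the plan says.** - **Rescue (section 8).** Oral lorazepam, 1-2 mg and then titrated, is the typical choice, but "any benzodiazepine or tranquilising medication may be administered". On who chooses: "This medical decision lies with the full-time trial clinicians present at the time, all ILS trained". The bullet excludes no drug and refers to no other section. The same section says that tranquillisation is for use only when everything else has failed and that the pilot study never needed it.
- **Rescue (section 7.1).** Only one drug is named: "Injectable lorazepam, as a 'rescue medication', will be available", for severe panic that does not respond to psychological measures.
- **Contraindications (section 2.3.2).** The list for escitalopram has a class of QT-prolonging medicines, which includes "Antipsychotics: Haloperidol, Droperidol, Thioridazine" and, further along, risperidone and chlorpromazine. Haloperidol and the phenothiazines also appear in that section's list of escitalopram interactions.
- **Escitalopram safety (section 7.2.1).** The MHRA advice is that escitalopram should not be used in patients with known QT prolongation "or in combination with other medicines known to prolong the QT interval".
- **Timing (sections 2.1.2 and 2.6).** The first daily capsule is taken "the morning after the first dosing session and document exactly when it was taken". On the second session in condition 2: "After 3 weeks they will have a second 1mg psilocybin dosing day (without interrupting the daily escitalopram dosing schedule)".
- **Blinding (sections 12 and 13).** The dispensing pharmacy withholds the allocation from the study team. The investigator may break the blind alone in a medical emergency, using sealed envelopes kept on site.

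**The concern.** Section 8 is what staff will follow when a patient is acutely disturbed. It gives an open permission, while two other sections of the same protocol warn against combining some of the permitted drugs with one of the trial treatments. The clinicians who apply it at the second session do not know who is taking that treatment. A clinician acting within section 8 could therefore give a QT-prolonging antipsychotic to a patient on escitalopram, and nothing in the bullet would prompt a check of section 2.3.2 or use of section 13. What is at stake is patient safety in a rare event, not the trial's inference.

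**Working it through.** The protocol gives no figure on this point to reproduce. The check compares the texts and the timing, with one count.

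**1. Do the permitted and the contraindicated drugs overlap?** Section 8 permits any tranquillising drug. Haloperidol, droperidol and chlorpromazine fall within that wording on a literal reading, and all three are on the section 2.3.2 QT list. Section 8 has no exception for them. The texts therefore overlap, although section 8 names no antipsychotic.

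**2. Does the section 2.3.2 list apply during the trial?** Mostly it deals with medication that patients bring with them: those taking a listed interacting drug stop it or may be excluded. But its NSAID entry asks for avoidance while the trial runs, so the list is not purely a screening tool. The advice in section 7.2.1 concerns the combination itself. The safeguard given there is the screening ECG, which cannot deal with a drug first given at Visit 5. An extra ECG and stopping escitalopram are foreseen only after signs of arrhythmia.

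**3. When can the combination occur?**

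| Session | Condition 1 (25 mg psilocybin) | Condition 2 (1 mg psilocybin) |
|---|---|---|
| Session 1 (Visit 3) | no escitalopram | none yet; first capsule about 8am next day |
| Session 2 (Visit 5) | placebo capsules | escitalopram 10 mg daily for 3 weeks, not interrupted |

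Concurrent exposure is therefore at session 2. Session 1 keeps a small residual question: if a listed drug were given late that day, nothing in the protocol delays the next morning's capsule. Whether the two drugs would then overlap depends on half-lives that the protocol does not give.

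**4. How many sessions are exposed?** Inputs: 60 completers, 30 per condition (section 4.2.1), two sessions each.

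- Planned sessions: 60 × 2 = 120.
- Sessions with the patient on escitalopram: 30 × 1 = 30, and 30/120 = 25%.
- Among session 2 visits alone: 30/60 = 50%.

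These are counts of patients on escitalopram. They are not rates of rescue, and the protocol gives no figure from which such a rate could be derived.

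**5. What has to happen for harm?** All of the following: a patient becomes disturbed on 1 mg psilocybin, which section 2 expects to be sub-psychoactive; de-escalation fails; lorazepam is inadequate or is passed over; a listed drug is chosen despite sections 2.3.2 and 7.2.1; and the blind is not broken first. Each step is unlikely. The first is not impossible, because section 7.2.1 lists agitation or restlessness as common with escitalopram (about 10%, quoted at 20 mg and not at the 10 mg taken by Visit 5).

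**The case against.** The strongest reply is that there is no contradiction. Section 8 permits and does not instruct. Section 2.3.2 sits under recruitment and is not a rescue formulary. The clinicians are bound by the whole protocol, which warns of the combination in sections 2.3.2 and 7.2.1 and puts lorazepam first in sections 7.1 and 8. Blinding does not defeat their judgement, because they can treat every Visit 5 patient as though on escitalopram. Section 13 already lets them unblind at once. On this view only a cross-reference is missing.

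Much of this stands, and it shows why several stronger readings fail:

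- **That the protocol directs staff to give a contraindicated drug.** It does not. The permission is merely unrestricted.
- **That blinded staff cannot protect the patient.** They can, by assuming exposure. Section 8 simply does not tell them to.
- **That a quarter of sessions are at risk.** The 25% counts escitalopram exposure, all of it in the arm least likely to need rescue from psilocybin effects.
- **That the listed drugs should be barred at Visit 5 unless unblinding shows no escitalopram.** Blinded staff would have to apply this to 25 mg patients too. They are the likeliest to need rescue and are not on escitalopram, and a compulsory step would be added in an emergency.
- **That session 1 needs no provision.** The next-morning capsule means that the protocol cannot support this.
- **That the lack of a scheduled ECG between Visits 1 and 7 is part of the fault.** It is a separate monitoring preference.

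The reply does not remove the mismatch. Section 7.2.1 warns against the combination whenever it occurs, and section 2.3.2 reaches beyond entry. An emergency instruction should not leave staff to reconcile it with other sections under pressure.

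**Conclusion.** The point holds as a minor patient-safety inconsistency. Section 8, read literally, allows rescue drugs that sections 2.3.2 and 7.2.1 advise against with escitalopram, and the overlap arises mainly at dosing session 2 in condition 2. The risk is very low and cannot be expressed as a rate from this document. The conclusion rests on reading the permission literally, on the planned 30 patients per condition attending both sessions, and on escitalopram being taken as scheduled. It has no bearing on the primary endpoint, sample size, bias or analysis. It is a cheap improvement, not a flaw that should hold up the trial.

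**What to change.** Replace the open permission in the section 8 bullet with wording such as:

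> Rescue is lorazepam or another benzodiazepine. At dosing session 2, treat every patient as possibly on escitalopram and avoid the QT-prolonging drugs listed in 2.3.2. If benzodiazepines are inadequate, use a tranquilliser not on that list, or consider unblinding under section 13 before using a listed drug; the final decision rests with the clinician. If a listed drug is given at session 1, review the start of the daily capsules.

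This brings sections 2.3.2, 7.1, 7.2.1, 8 and 13 into line and keeps an emergency option for every patient. The cost is the edit to one bullet, a slightly narrower first choice of rescue drug at Visit 5 and, rarely, an unblinding before the week-6 endpoint.

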## 9. Purchasing, manufacturing and storing drug

Psilocybin free-base will be purchased and made to Good Manufacturing Practice standards in accordance with Medicines and Healthcare Products Regulatory Agency (MHRA) regulations. The drug will be stored in a secure laboratory in a locked fridge. Home Office permission for possession and storage will be obtained.

The API psilocybin is being synthesised to GMP standard by Onyx pharmaceuticals (UK) and encapsulated to GMP standards by Juniper pharmaceuticals (UK) and blinded by Fisher pharmaceuticals (UK). This route will provide both the 25mg and 1mg doses of psilocybin for the dosing session. Regarding 6 weeks of escitalopram versus 6 weeks of placebo, relevant doses of escitalopram and placebo are to be encapsulated in accordance with GMP guidelines by Guys and St Thomas' (GSTT) manufacturing pharmacy (UK). Labelling will be done entirely by GSTT. All of the relevant parties possess Home Office schedule 1 drugs licenses.

## 10. Analysis

The data collected from this study will be used to gather new information and inform future studies. Data will be tabulated and descriptive parameters derived. The study is powered for a baseline vs week 6 t-test on the QIDS-16 (condition 1 vs condition 2) and this is the primary efficacy outcome and endpoint.

## 11. Dosing procedure and patient management

It is strongly advised that psychedelic drugs only be taken in a positive environment where the patient feels comfortable and relaxed [70]. Efforts will be made to arrange the intervention room to promote relaxation without compromising medical safety. Mobile phones will be switched off during every session and efforts will be made to minimize unexpected interruptions.

Patients will arrive in the morning at 9am but the dosing itself will take place at 10:30am. Patients will have been strongly advised to refrain from alcohol for a minimum of 24 hours prior to their arrival as alcohol may compound the effects of the drug and potentially interfere with its effects. Patients will be psychologically prepared for the experience at screening. We will advise the patient to surrender to the experience and relaxing music will be used to facilitate calm and a relaxed, accepting mind-set. We will caution patients to expect some anxiety, and they will be encouraged to let us know if they feel this. Consistent with published guidelines on managing psychedelic-drug sessions, patients will be advised to accept feelings of anxiety and to allow the experience to unfold naturally, without psychological resistance [70].

Based on our experience in the feasibility study, we will not initiate conversation with the patient. However, we will respond to them if they initiate contact. It is advised that active intervention is kept to a minimum during the acute experience. The patient is encouraged to explore their own mental space. Simple guided imagery may be used to assist relaxation.

Sessions will take place in a purpose built clinical research facility with extensive nursing and emergency support, Invicro (previously called Imanova). All sessions will be supervised by at least 2 individuals. A study medical doctor will administer the drug/placebo and be available on site during the dosing sessions. If required, he/she can attend the therapy room within less than 5 minutes.

After approximately 5 hours post dose, most of the acute subjective effects of psilocybin will have subsided and we will begin a thorough debriefing. This will involve encouraging the patient to give a detailed descriptive account of the experience. With the patient's prior consent, dosing sessions will be video and/or audio recorded. Post-session interviews will also be video and audio recorded for qualitative analyses. At the end of the dosing day, a study medical doctor will assess the patient for potential discharge and the relevant capsules of escitalopram or placebo will be given, depending on the results of the randomisation.

